8. RESEARCH QUESTION AND OBJECTIVES

The research question for this study is: What is the risk of pregnancy outcomes of interest, and infant outcomes of interest, among pregnant women exposed to PAXLOVID, exposed to other COVID-19 therapies, and among pregnant women with COVID-19 unexposed to any therapies?

The primary objective of this study is to estimate the risk of MCM among pregnant women who are exposed to PAXLOVID (and not other COVID-19 treatments) during pregnancy (Cohort 1), pregnant women not exposed to PAXLOVID but exposed to other COVID-19 treatments (Cohort 2), and pregnant women with COVID-19 not exposed to any COVID-19 treatments (Cohort 3).

The secondary objectives of this study are to:

- 1. Estimate the risk of pregnancy outcomes (SA, induced termination, stillbirth, livebirth) and the risk of infant outcomes (SGA, preterm birth, postnatal growth deficiency, and infant developmental delay) for livebirths among the 3 study cohorts.
- 2. Pending sufficient sample size (Section 9.5), to compare the risk of pregnancy and infant outcomes in Cohort 1 compared to Cohort 2, and Cohort 3, separately.

9. RESEARCH METHODS

9.1. Study design

This 5-year observational cohort study will use administrative healthcare claims data (the ORD) to assess PAXLOVID exposure and pregnancy and infant outcomes including SA, induced termination, stillbirth, livebirth, SGA, preterm birth, postnatal growth deficiency, and infant developmental delay and MCM. The primary outcome is MCM, which will be confirmed via medical record review. Pregnancies that begin (based on the ECD, equal to LMP + 14 days) between 01 March 2021 and 01 December 2025 will be identified. For the assessment of infant outcomes, pregnancies that begin on or before 01 April 2025 will be eligible for inclusion. Pregnancies that began in March 2021 are the earliest eligible PAXLOVID-exposed pregnancies in the US (ie, potentially exposed to PAXLOVID close to delivery in December 2021).

All qualifying pregnancies per woman will be included in the study and classified according to the COVID-19 treatments received during 2 relevant exposure windows:

- First trimester exposure window
- Full pregnancy exposure window

These 2 windows provide the flexibility to assess the timing of exposure during pregnancy, as the relevant etiologic period may be the first trimester for MCM whereas the full pregnancy may be the relevant exposure period for pregnancy or other infant outcomes. Given that COVID-19 treatment is typically administered shortly after COVID-19 diagnosis, these exposure windows will account for timing of COVID-19 during pregnancy as well.

[figure not shown]
Based on received COVID-19 treatments during each of 2 exposure windows (first trimester, pregnancy), the pregnancies will be classified into the following exposure cohorts (for a total of 6 cohorts):

- Cohort 1 (PAXLOVID cohorts): at least 1 dispensing of PAXLOVID within the relevant exposure window, and no evidence of comparator medications within the relevant exposure window
- Cohort 2 (Treated Comparator Only cohorts): no evidence in the study database of a dispensing of PAXLOVID, and dispensing or administration of at least 1 of the following treatments indicated for the treatment of mild-to-moderate COVID-19 within the relevant exposure window:
 - Remdesivir
 - Bebtelovimab
- Cohort 3 (Untreated Comparator cohorts): no evidence in the study database of a dispensing or administration of any COVID-19 treatments within the relevant exposure window

The exposure cohorts will be defined separately for each exposure window, so that each pregnancy will be assigned an exposure cohort based on the first trimester window, and an exposure cohort based on the full pregnancy window. Women who receive PAXLOVID plus another COVID-19 treatment during pregnancy will be excluded. As some women may receive multiple COVID-19 treatments during pregnancy, the number of pregnancy episodes excluded due to exposure to more than 1 type of medication (eg, PAXLOVID followed by remdesivir) will be reported. Presence of COVID-19 and exposure to COVID-19 treatments will be identified through reimbursement of medical or pharmacy services. Exposure during relevant windows will be determined by pharmacy dispensings (or drug administrations) of the corresponding COVID-19 treatments and the days' supply (or recommended administration schedule), in addition to time to nondetectable concentration of the COVID-19 treatments based on 5x the clearance half-life.

For the assessment of pregnancy outcomes (ie, SA, induced termination, stillbirth, livebirth), pregnancies that begin on or before 01 December 2025 (the final day of accrual) will be followed through the end of pregnancy, as data allow (Figure 1).

[figure not shown]
Figure 1. Study Overview for Pregnancy Outcomes

^{*}Earliest data, as available

For the assessment of infant outcomes, pregnancies that begin on or before 01 April 2025 will be eligible for inclusion. Infant follow-up will occur through the first year of an infant's life (Figure 2). To assess infant outcomes, the subset of women whose pregnancy results in livebirth(s) will be linked to their infants' available data.

Figure 2. Study Overview for Infant Outcomes

^{*}Earliest data, as available

During the accrual period, pregnancies that qualify for the exposure cohorts will be identified annually and described with respect to baseline characteristics such as length of health plan enrollment, use of relevant medications, and comorbidities. Counts of outcomes, and the subset of outcomes eligible for medical record review, will be included in annual reports. Accrued pregnancies will also be assessed on an annual basis to determine whether there will be sufficient statistical power to detect a difference in risk across the study cohorts with respect to the outcomes of interest.

At the end of the study follow-up period, propensity scores that discriminate between use and non-use of PAXLOVID (separately for each comparator cohort and relevant exposure window) will be created from a wide variety of demographic, baseline comorbidity, disease severity, and co-medication indicators, as well as risk factors for the study outcomes. The propensity scores will be used to adjust for confounding via IPTW. Pending sufficient sample size, the prevalence of the pregnancy and infant outcomes among pregnant women who were exposed to PAXLOVID only will be contrasted with the 2 comparator cohorts.

Pregnancy and infant outcomes will be assessed using claims-based algorithms from the literature with adequate positive predictive values (PPVs) when available, otherwise confirmed via medical records. Given that most pregnancies result in a livebirth, a sample of livebirths will be selected for medical record confirmation of livebirth.

9.2. Setting

The base population for this study will include pregnancies that began (based on ECD) between 01 March 2021 and 01 December 2025, among women treated for COVID-19 or with a COVID-19 diagnosis.

9.2.1. Inclusion criteria

Pregnancies will be eligible for inclusion if they have complete medical coverage and pharmacy benefits and continuous enrollment for at least 6 months prior to ECD. Longer baseline periods (eg, 12 months) will allow for more complete capture of underlying conditions (eg, pregnancy outcome risk factors), at the potential cost of smaller sample sizes. Such factors will be considered and explored before finalization of the baseline period duration in the SAP, which will be dated, filed, and maintained by Pfizer. Pregnancies will be classified into the exposed and comparator pregnancy cohorts according to COVID-19 treatments received during pregnancy.

Patients must meet all of the following inclusion criteria for the pregnancy to be eligible for inclusion in the study:

- 1. Age 12 to 49 years at ECD
- 2. ECD between 01 March 2021 and 01 December 2025
- 3. Continuous medical and pharmacy coverage for a minimum of 6 months prior to and including the ECD

Pregnancies meeting all of the inclusion criteria will be included in the base population, with the cohort entry date set to the ECD. Additional criteria for inclusion in the study cohorts are described in Section 9.2.6.

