7. RATIONALE AND BACKGROUND

On 22 December 2021, the US FDA granted Pfizer's antiviral PAXLOVIDTM EUA for mild-to-moderate COVID-19 in patients aged 12 years or older who are at high risk for progression to severe COVID-19. On 25 May 2023, the US FDA granted full approval for PAXLOVID under the same indication among patients aged 18 years or older (FDA 2023). Pregnant patients are considered at high risk for progression to severe COVID-19 (CDC 2022).

PAXLOVID, the first FDA-authorized oral COVID-19 antiviral (FDA 2021), is a combination of 300 mg nirmatrelvir (two 150 mg tablets) and 100 mg ritonavir (one 100 mg tablet) all taken together orally twice daily for 5 days (Pfizer 2022). Nirmatrelvir is the first severe acute respiratory syndrome coronavirus 2 (SARS-CoV-2) 3-chymotrypsin–like (3CL) cysteine protease (also known as Mpro) inhibitor. Ritonavir is co-administered at a low dose as a pharmacokinetic (PK) enhancer, to inhibit the CYP3A metabolism of nirmatrelvir and increase plasma concentrations to allow for twice daily dosing (Pfizer 2022). Ritonavir was approved in the US in 1996 for human immunodeficiency virus (HIV) (Schouten et al. 1996).

The Phase 2/3 trial, Evaluation of Protease Inhibition for COVID-19 in High-Risk Patients ("EPIC-HR"), examined PAXLOVID safety and efficacy among non-hospitalized COVID-19 patients. Interim analyses observed an 89% lower risk of hospitalization or death compared to placebo when PAXLOVID was initiated within 3 days of symptom onset (Pfizer 2021).

There is limited data on the safety of PAXLOVID in pregnant women and their offspring (Garneau et al. 2022, Loza et al. 2022). In addition, there are currently no available human data on the use of nirmatrelvir during pregnancy to evaluate a drug-associated risk of major

birth defects, miscarriage, or other adverse maternal or fetal outcomes (Pfizer 2022). Published observational studies on ritonavir use in pregnant women did not identify an increase in the risk of major birth defects (APRSC 2012, Pasley et al. 2013).

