9.2.6.2. Cohort 2: Treated comparator only cohorts

Pregnancies will be included in the Treated Comparator Only cohorts (Cohort 2) if they meet the following criteria:

- 1. Any of the following:
 - a. Administration of remdesivir in an outpatient setting between 9 days prior to ECD and the end of the exposure window.

OR

b. Administration of bebtelovimab in an outpatient setting between 60 days prior to ECD and the end of the exposure window.

AND

2. No dispensing of PAXLOVID (any setting) between 12 days prior to first eligible comparator drug dispensing and the end of the exposure window.

The 9-day pre-ECD window for remdesivir was chosen because of the 3-day recommended treatment course and 6 days to achieve 5x the clearance half-life (FDA 2022b). The 60-day pre-ECD window for bebtelovimab was chosen because of the 60-day requirement to achieve 5x the clearance half-life (FDA 2022c).

Pregnancies with exposure to more than 1 Cohort 2 medication (eg, a pregnancy exposed to both remdesivir and bebtelovimab, or other future approved or authorized COVID-19 therapies included in Cohort 2) will be eligible for inclusion.

Lists of approved or authorized COVID-19 therapies for the definition of the treated comparator will be periodically reviewed and updated in the SAP as necessary.

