9.2.6.3. Cohort 3: Untreated comparator cohorts

Pregnancies will be included in the Untreated Comparator cohorts (Cohort 3) if they meet the following criteria:

1. At least 1 COVID-19 diagnosis (ICD-10 U07.1) in an outpatient, inpatient, or emergency room setting between 7 days prior to ECD and the end of the exposure window.

AND

- 2. No exposure to any authorized COVID-19 therapies, regardless of setting (ie, outpatient/inpatient). Authorized therapies used to exclude pregnancies from the unexposed cohorts include:
 - a. Study cohort drugs
 - b. Other approved or authorized treatments (eg, molnupiravir, other monoclonal antibodies)
 - c. Convalescent plasma (indicated for patients with immunosuppressive disease or receiving immunosuppressive treatment)

Lists of authorized COVID-19 therapies for the exclusion definition of the untreated comparator cohort will be periodically reviewed for completeness and updated in the SAP as necessary and will include all approved or authorized (EUA for the treatment of mild-to-moderate COVID-19) medications at any point during the study period. Medication-specific pre-ECD windows for exclusion for other monoclonal antibodies and convalescent plasma will be based on typical treatment durations and medication half-lives (as with other study cohort treatments) and defined in the SAP.

9.2.7. The index date for Cohort 3 will be the date of COVID-19 diagnosis plus the treatment interval (the median interval between COVID-19 diagnosis and treatment in Cohort 1; as defined in Section 4.3.3.1.1 in the SAP)Follow-up

For the assessment of pregnancy outcomes, follow-up for each pregnant woman will extend from the day following cohort entry (ECD) until the earliest of: disenrollment from the health plan, end of the pregnancy, or 01 September 2026.

For the assessment of infant outcomes, linked infants (the subset of pregnancies resulting in livebirths that are linked to the mother's data) will be followed from the date of delivery until the earliest of: disenrollment from the health plan or 1 year of age.

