9.7.2.1.1. Inverse probability of treatment weighting

Propensity scores will be used to calculate IPTW weights and to weight each pregnancy in the exposure cohorts. For the IPTW analysis, a sample of comparators may be selected if a large number of pregnancies is accrued into the comparator cohorts (particularly the Untreated Comparator cohorts). This would be done to improve study efficiency through reducing the number of potential medical records to be sought among the comparator cohorts. If implemented for the final analysis, up to 5 comparators per PAXLOVID-exposed pregnancy will be sampled. Sampling of comparators will be performed via random sampling, without replacement, within strata of maternal age and calendar time based on the distributions within the PAXLOVID cohort. Sampling in this manner ensures that comparator pregnancies are approximately matched, at ECD, on the important covariates of maternal age and calendar time.

The IPTW weights will be defined such that the causal estimate is the average treatment effect among the treated (ATT) (Austin & Stuart 2015). Briefly, to estimate the ATT, the weights (w_{ATT}) are defined such that every PAXLOVID-exposed pregnancy receives a weight of 1, while the comparator pregnancies receive weights that are a function of the propensity score:

$$w_{ATT} = Z + \frac{\mathrm{e}(1-\mathrm{Z})}{1-\mathrm{e}},$$

where Z is the indicator for PAXLOVID exposure, e is the propensity score, and X is the covariate pattern used to predict PAXLOVID exposure (Section 9.7.2.1):

$$e = \Pr(Z = 1 | X).$$

Balance of covariates among the weighted cohorts will be assessed using the weighted standardized difference ($SD_{weighted}$) comparing the weighted study cohorts. Any variables with an absolute $SD_{weighted} > 0.1$ may be considered imbalanced. If specific variables remain imbalanced after IPTW, they may be included as independent predictors in outcome models. Trimming of extreme weights will be considered (Stürmer et al. 2014).

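### Calendar eligibility rests on conception date alone, so the comparator cohorts' pooled crude risks and crude ratios can include COVID-19 episodes from before PAXLOVID was authorised

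*Protocol*

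**What the plan says.** Protocol Section 9.2.1 limits the base population by conception date, "ECD between 01 March 2021 and 01 December 2025", "with the cohort entry date set to the ECD". Section 9.1 gives the reason for the start: "Pregnancies that began in March 2021 are the earliest eligible PAXLOVID-exposed pregnancies in the US". Section 7 dates the emergency authorisation: "On 22 December 2021, the US FDA granted".

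The cohort definitions are tied to the ECD and set no calendar date of their own. Cohort 3 (Section 9.2.6.3) needs a COVID-19 diagnosis "in an outpatient, inpatient, or emergency room setting between 7 days prior to ECD and the end of the exposure window". Cohort 2 (Section 9.2.6.2) admits "Administration of remdesivir in an outpatient setting between 9 days prior to ECD and the end of the exposure window", or outpatient bebtelovimab from 60 days before ECD.

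Four provisions deal with calendar time:
- Section 9.3.3.2.1 lists month and year of the index date as a baseline covariate, beside month and year of ECD.
- Section 9.7.2.1 commits the propensity score models to include calendar time and names the change from Delta to Omicron.
- Section 9.7.4.7 plans descriptive and comparative analyses by calendar time of first treatment or infection.
- Section 9.7.2.1.1 allows up to 5 sampled comparators per exposed pregnancy, so that "comparator pregnancies are approximately matched, at ECD, on the important covariates of maternal age and calendar time".

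The prevalences reported for each cohort are crude (Section 9.7.2.2). Section 9.7.2.3 reports crude ratios beside the IPTW-adjusted ones.

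**The concern.** The start date was chosen so that women treated with PAXLOVID near delivery in December 2021 are not missed. That reason has no bearing on Cohorts 2 and 3, yet the same window governs them. A woman who conceived in spring 2021 and had COVID-19 that summer qualifies for Cohort 3, although PAXLOVID was not available to her.

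The primary objective (Section 8) is the MCM risk in each of the three cohorts, estimated without weighting. If Cohort 3 pools episodes from before and after authorisation, its risk describes a different period from Cohort 1's, and a crude ratio between them confounds drug with era. By Section 9.7.2.1's own account, prescribing, variants and severity changed over that time.

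**Working it through.** **Inputs.** First eligible ECD 01 March 2021 (Section 9.2.1). Authorisation 22 December 2021 (Section 7). Pre-ECD windows of 7 days for a Cohort 3 diagnosis and 9 days for Cohort 2 remdesivir (Sections 9.2.6.3 and 9.2.6.2). ECD = LMP + 14 days (Section 9.1).

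**The plan's own start date.** Gestational age on 22 December 2021 is days since ECD plus 14.
- ECD 31 March 2021: 266 + 14 = 280 days = 40w0d.
- ECD 17 March 2021: 280 + 14 = 294 days = 42w0d.
- ECD 01 March 2021: 296 + 14 = 310 days = 44w2d.

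March 2021 is therefore right to the month for Cohort 1. Only ECDs of 01 to 16 March would need a pregnancy longer than 42 weeks.

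**Longest lead before authorisation.** Lead = 22 December 2021 − (01 March 2021 − pre-ECD window).
- Cohort 3: from 22 February 2021, 296 + 7 = 303 days.
- Cohort 2, remdesivir: from 20 February 2021, 296 + 9 = 305 days.

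**First-trimester cohorts.** A Cohort 1 member needs a first trimester that reaches 22 December 2021. Its length is an assumption here, taken as ending 12 to 14 weeks after LMP, which is 70 to 84 days after ECD.
- Ends at 14 weeks: earliest possible Cohort 1 ECD is 22 December − 84 days = 29 September 2021. ECDs from 01 March to 28 September, 212 days, have no possible Cohort 1 member.
- Ends at 12 weeks: 22 December − 70 days = 13 October 2021. ECDs from 01 March to 12 October, 226 days, have none.

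The ECD range for infant outcomes, 01 March 2021 to 01 April 2025, is 1,493 days, so this is 212/1,493 = 14% to 226/1,493 = 15% of eligible calendar days. These are days, not pregnancies.

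**What weighting does.** The ATT weight for a comparator is e/(1 − e), which tends to 0 as e tends to 0. In index months when nobody could receive PAXLOVID, a model that represents index time flexibly should fit e near 0, so those women nearly vanish from the weighted ratio. A smooth time term could leave them some weight. The crude prevalences and crude ratios use no weights, so each such woman counts fully.

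**What sampling on ECD does.** Take ECD 01 August 2021 in the full-pregnancy window as an illustration. On 22 December the pregnancy is 143 days past ECD, 143 + 14 = 157 days = 22w3d. A Cohort 1 member with that ECD must have an index date on or after 22 December. A Cohort 3 pregnancy with the same ECD can have its diagnosis from 25 July 2021, 143 + 7 = 150 days earlier. The two agree on ECD but not on date of infection.

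**The case against.** The strongest reply is that the plan already handles time. Index month and year is a listed covariate, calendar time enters the propensity score, and Section 9.7.4.7 promises descriptive as well as comparative results by calendar time of infection or treatment. The adjusted comparison is a secondary objective. Section 9.9 values Cohort 3 as a background rate in diagnosed pregnant women and admits its limited exchangeability. Most of this stands: bias in the weighted ratio should be small, and era-specific descriptions should be available. It does not reach the pooled crude risks that answer the primary objective, or the crude ratios. A rate that mixes eras is also not the background for PAXLOVID-era pregnancies.

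Four stronger readings are tempting, and the documents do not support them.
- A reader might take the 2021 column of Table 3 (19,581 of 24,966 COVID-19-positive pregnancies in 2021 to mid-2022) as the pre-authorisation share. The table is not split by diagnosis date. Its 2021 column also holds 295 PAXLOVID pregnancies, too many to be plausible for the ten days from 22 to 31 December, so the columns probably follow pregnancy timing. The table also stops at mid-2022, while accrual runs to December 2025.
- A reader might say that the March 2021 rationale fails because an ECD of 01 March gives 44w2d. The statement is made at the level of the month and holds there.
- A reader might infer that Cohort 2 is largely pre-PAXLOVID. Section 7 says that bebtelovimab availability substantially overlapped PAXLOVID's. Remdesivir counts only if given to outpatients, and Table 3 does not give the setting.
- A reader might infer that sampling and chart requests are wasted on unmatched first-trimester comparators. If sampling is used, its strata follow the PAXLOVID cohort's distribution, so ECD strata without Cohort 1 members would yield none. The misalignment remains only in the full-pregnancy cohorts, and its size is not shown.

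**Conclusion.** The point holds as a cheap improvement. Eligibility is anchored on ECD for a reason specific to Cohort 1, and nothing keeps comparator index dates within the period when PAXLOVID could be dispensed. Cohort 3 can reach back 303 days before authorisation. Cohort 2 can include earlier outpatient remdesivir, in a number that cannot be determined from the protocol. About seven months of first-trimester ECDs (212 to 226 days, given a first trimester ending 14 to 12 weeks after LMP) can supply only comparators.

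The consequence is confined to the pooled crude cohort risks, the crude prevalence ratios, and any ECD-based sampling in the full-pregnancy cohorts. The expectation that the weighted ratio is little affected assumes that index calendar time is kept in the propensity score and modelled flexibly. The share of Cohort 3 pregnancies involved, and the resulting shift in MCM risk, cannot be computed from the protocol.

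**What to change.** In Section 9.2.6, add for all three cohorts and both exposure windows that the index date must be on or after 22 December 2021. The index date is the treatment date for Cohorts 1 and 2, and the diagnosis date plus the treatment interval for Cohort 3. Keep the ECD window as the outer limit. In Section 9.7.2.1.1, stratify any comparator sampling on calendar time of the index date instead of the ECD.

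This removes the pre-authorisation span entirely and needs one eligibility line and one sampling line. The cost is a smaller Cohort 3, for which Section 9.7.2.1.1 already foresees a possible surplus, and the loss of any pre-authorisation Cohort 2 pregnancies. Cohort 2 is the scarcer group (about one per five PAXLOVID pregnancies, Section 9.5), so the number lost should be reported. Those pregnancies should carry almost no weight in the adjusted comparison. Because the change alters the populations behind the primary estimates, it should be made by protocol amendment before the final analysis.
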